8.1 Adverse Events

Treatment-emergent adverse events (TEAEs) are AEs that are not present prior to the exposure to study treatment. All AEs reported following exposure to study treatment are considered TEAEs. All TEAEs will be coded using the Medical Dictionary for Regulatory Activities (MedDRA) Version 25.0. The listing and summaries will include coded System Organ Class (SOC) and Preferred Term (PT).

An overall summary by treatment (dose level of AL001 and pooled placebo and overall) will present the number and percentage of subjects with:

- At least one TEAE
- At least one drug-related TEAE
- Severity intensity

- Mild
- Moderate
- Severe
- Life-threatening
- Death
- at least one SAE
- at least one drug-related SAE
- death

For the study, the following AE tables will also be presented:

- TEAEs by SOC and PT
- SAEs by SOC and PT
- Drug-related TEAEs by SOC and PT
- TEAEs by SOC, PT, and maximum intensity
- TEAEs that lead to premature discontinuation

Events will be listed by treatment, subject and AE onset date. Treatment-emergent AE duration (stop date/time - start date/time) will be included in the listing.

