
Summary - Conclusions
 
Pharmacokinetic Results:
 
The observed AL001 MTD (the Cohort 4a/4b dosing level, 1680 mg given TID at 8 AM, 2 PM, and 8 PM, total daily dose 5040 mg) provided lithium at a lithium carbonate equivalent dose of 240 mg TID (720 mg daily) or a lithium citrate oral solution or syrup (8 mEq/5 mL) equivalent dose of 4 mL TID (19.2 mEq daily), all under fasted conditions. With respect to salicylate, these levels of exposure can be justified as safe a posteriori since they are less than the maximum for prescriptive aspirin/salicylate indications and are to be used for a serious medical condition. There were no undue safety concerns identified in the AL001-ALZ02 Study and so none were considered to be related to PK exposures. The MTD was selected to mitigate or obviate the need for AL001 therapeutic drug monitoring (TDM) in targeted neurodegenerative, neurological, and neuropsychiatric conditions, at least for subjects without undue renal compromise.
 
Under the conditions of this study, no clinically obvious or relevant lithium or salicylate PK differences were observed between non-elderly and elderly healthy subjects.
 
There were no obvious demographic characteristics observed under the conditions of this study that can be used to improve future enrollments when screening subjects.
		

Safety Results:

AD Subject Cohorts

- No deaths or SAEs occurred during the study. No subject prematurely discontinued the study due to a treatment-emergent AE (TEAE).
- AL001 was well tolerated in AD subjects regardless of their comorbidities and concomitant medications.
- A total of 24 TEAEs were experienced by 12 of 25 subjects who received AL001 and 6 TEAEs were experienced by 4 of 8 subjects in the pooled placebo group. The proportion of AD subjects with TEAEs increased with increasing dose levels of AL001, with the lowest proportions of subjects in Cohorts 1 (14.3%; AL001 1890 mg) and 2b (16.7%; AL001 3150 mg), and the highest proportion observed (83.3%) in Cohorts 3b (AL001 4410 mg) and 4b (AL001 5040 mg). The proportion of subjects with TEAEs in the pooled placebo group (50.0%) was between that observed in AL001 Cohorts 2b and 3b.
- All TEAEs were experienced by only 1 subject who received either AL001 or placebo, except headache (1 of 6 subjects [16.7%] each in Cohorts 3b and 4b) and pollakiuria (2 of 6 subjects [33.3%] in Cohort 4b).
- No AEs of special interest were reported for AD subjects.

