2 STUDY OBJECTIVES

The objectives of the study and corresponding study endpoints are detailed in Table 1.

Table 1: Objectives and Related Endpoints

Objective	Endpoint	Analysis
Primary		
To evaluate the safety and tolerability of AL001 under multiple-dose, steady-state conditions in Alzheimer's subjects and healthy adult subjects.	
 • Vital signs (blood pressure, heart rate, and oral body temperature) • 12-lead electrocardiogram • Physical examination • Safety laboratory tests (hematology, chemistry [including thyroid-stimulating hormone (TSH), vitamin B12, and Mg], HbA1c, and urinalysis • Reported and observed Adverse events (AEs)/serious AEs)/tolerability observations including signs and/or symptoms of lithium and/or salicylate toxicity 	Refer to Section 8
Secondary		
To characterize the Maximum tolerated dose (MTD) of AL001 in patients with mild to moderate Alzheimer's disease (AD) and healthy adult subjects.	
 • Prevalence of peak salicylate concentrations above 30 mg/dL • Prevalence of trough plasma lithium concentrations above 1.2 mEq/L for healthy adult subjects or 1.0 mEq/L for healthy elderly and Alzheimer's subjects. 	Refer to Section 7
Exploratory		
To explore the difference in PK profile between the non-elderly vs elderly subjects (healthy subjects only).	
 • Descriptive statistics for PK will be presented by treatment group and compared between non-elderly and elderly subjects. 	Refer to Section 7

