8 SAFETY ANALYSIS

Unless otherwise specified, all available data will be listed and summary tables for safety assessments will be presented by treatment (dose level of AL001 and pooled placebo) per cohort for the safety population as detailed in Table 5 and all applicable safety data will be presented by combined active and pooled placebo groups, such as, disposition, demographic, adverse events, labs, vital signs, and 12-ECG data.

Continuous variables will be summarized (absolute values and change from baseline) using descriptive statistics (n, mean, SD, minimum, median and maximum).

Table 5: Data Presentations for Safety Assessments

Data	Variables	Presentation
Adverse events	Adverse event (AE) description, date and time (start and end), intensity, relationship to study drug, action taken, study days and outcome	Listing Table
Extent of exposure	Study drug administration dose, units, date, time, cohort	Listing
Clinical laboratory evaluations	Laboratory results (refer to section 8.3 for parameters)	Listing Table
Vital signs	Blood pressure, pulse, and body temperature	Listing Table
Physical examinations	Physical examinations findings	Listing
12-Lead ECGs	ECG interpretations and findings	Listing Table

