⁶ Blood samples for baseline plasma lithium and plasma salicylate concentration measurements will be collected before first dose on Day 1. Blood samples for trough plasma lithium and peak plasma salicylate concentration measurements will be collected on Days 3, 5, 7, 10, 13, and 14, and at the discretion of the Investigator (the latter are 'Safety Samples' for Therapeutic Drug Monitoring), particularly to assess the relationship to possible lithium or salicylate related AEs. These safety samples could be sent for expedited analysis to either a local laboratory with an aliquot saved for the bioanalytical laboratory, or to the bioanalytical laboratory directly (Sannova or Altasciences). In addition, for AD subject Cohorts 2b, 3b, 4b, and 5b, the trough lithium sample on Day 5 will be treated as a 'Safety Sample' for Therapeutic Drug Monitoring to assess any lithium-related PK exposure safety concerns at an early treatment time point which may require dosing to be discontinued for an individual subject. This sample will be sent to Sannova for expedited analysis. Similarity between Days 13 and 14 trough lithium plasma levels and peak salicylate plasma levels will be used to determine the status of lithium and salicylate steady-state PK conditions, and/or by another appropriate method, such as linear regression. Blood collection for trough lithium plasma concentrations will occur just prior to the first daily dose, while blood collection for peak plasma salicylate concentrations will occur at 1.25 hours post third daily dose (the estimated time to a maximum blood concentration C_{max}). For early termination, blood samples for lithium and salicylate plasma concentrations will be collected. A ±10-minute window will be allowed for collection of PK samples for both lithium and salicylate.

⁷ Hachinski Ischemic Scale Score is presented in protocol APPENDIX 5.

Study Procedures	Screening (28 days prior to randomization)	In-patient admission	Treatment Period		Clinic Discharge	Follow-up Period		Early Termination (ET)
Study Day	Days -28 to -1	Day -1	Day 1	Days 2 to 14	Day 15	Day 23 ±1 day Clinic Visit	Day 42 ±2 days Telephone call	
Adverse Event Reporting/Safety-Tolerability Assessment	X	X	X	X	X	X	X	X
Prior Medications	X	X						
Concomitant Medications	X	X	X	X	X	X	X	X
Health Status Questionnaire (SF-36)						X	X	X

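### SAP 8.1 defines a TEAE by two conflicting sentences, one with no provision for worsening, so TEAE counts may be too low or too high depending on which is programmed

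*SAP*

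**What the plan says.** SAP Section 8.1 (Adverse Events) gives the definition in two consecutive sentences:

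- First: "Treatment-emergent adverse events (TEAEs) are AEs that are not present prior to the exposure to study treatment".
- Second: "All AEs reported following exposure to study treatment are considered TEAEs".

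The SAP text supplied contains Section 8.1 twice, with the same two sentences each time. Neither sentence mentions worsening, and nothing ranks one above the other.

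Four other places bear on the point.

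- SAP Section 2, Table 1, puts AEs among the primary endpoints: "Reported and observed Adverse events (AEs)/serious AEs)/tolerability observations including signs and/or symptoms of lithium and/or salicylate toxicity". They stand beside vital signs, ECG, physical examination and laboratory tests.
- In SAP Appendix A, the row "Adverse Event Reporting/Safety-Tolerability Assessment" is marked from Screening and Day -1 through Day 42 and early termination.
- SAP Section 8, Table 5, plans to present "Adverse event (AE) description, date and time (start and end), intensity", among other variables. Section 8.1 adds: "Events will be listed by treatment, subject and AE onset date".
- SAP Section 9.1 gives a study-day formula for events that precede dosing and applies study days to the AE listings.

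The synopsis reports results on this count. For the AD cohorts it says: "A total of 24 TEAEs were experienced by 12 of 25 subjects who received AL001".

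**The concern.** Pre-dose AEs are foreseeable in this design. They are collected from Screening, subjects are in the unit for at least 16 hours before the first dose, and the SAP provides a study-day formula for them. A definition of treatment emergence has to say what happens to such an event when it is reported late and when it gets worse. Section 8.1 gives opposite answers to the first question and does not address the second.

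The overall TEAE summary and four of the five further AE tables in Section 8.1 are built on this flag; the SAE table is not expressly limited to TEAEs. The flag also supports the synopsis statement that "AL001 was well tolerated in AD subjects regardless of their comorbidities and concomitant medications". For a claim worded that way, aggravation of something already present is a relevant kind of event, and it is the kind that the first sentence does not provide for.

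**Working it through.** **Step 1. Apply each sentence to each type of event.**

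| Event | First sentence alone | Second sentence alone |
|---|---|---|
| Onset after first dose | TEAE | TEAE |
| Onset and report both before first dose, unchanged | Not a TEAE | Not a TEAE |
| Onset before, reported after, unchanged | Not a TEAE | TEAE |
| Onset and report before, intensifies after, no new AE recorded | Not a TEAE | Not a TEAE |
| Onset before, intensifies after, worsening recorded as a new AE | Unclear: the complaint was present before | TEAE |
| Medical-history condition worsens, recorded as an AE starting after dosing | TEAE, if the AE and not the condition is what must be absent | TEAE |

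The third row is a direct contradiction. The fourth and fifth rows show the missing worsening provision. The possible overcount belongs to the second sentence. The possible undercount belongs mainly to the first.

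**Step 2. Reproduce the reported counts.** The synopsis gives AD cohort proportions of 14.3% (Cohort 1), 16.7% (2b), 83.3% (3b) and 83.3% (4b), a total of 25 on AL001, and 4 of 8 on pooled placebo. With six on AL001 in each of 2b, 3b and 4b, Cohort 1 has 25 − 3 × 6 = 7, which fits 1/7 = 14.3%.

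- AL001: (1 + 1 + 5 + 5)/(7 + 6 + 6 + 6) = 12/25 = 48.0%.
- Pooled placebo: 4/8 = 50.0%.

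The figures are internally consistent.

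**Step 3. Sensitivity to one subject.** The shift is 1/n: 1/6 = 16.7, 1/7 = 14.3, 1/8 = 12.5 and 1/25 = 4.0 percentage points.

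| Group | Reported | One fewer | One more |
|---|---|---|---|
| Cohort 1 | 1/7 = 14.3% | 0.0% | 28.6% |
| Cohort 2b | 1/6 = 16.7% | 0.0% | 33.3% |
| Cohorts 3b, 4b (each) | 5/6 = 83.3% | 66.7% | 100.0% |
| All AL001, AD | 12/25 = 48.0% | 44.0% | 52.0% |
| Pooled AD placebo | 4/8 = 50.0% | 37.5% | 62.5% |

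One more AL001 subject (52.0% against 50.0%) or one fewer placebo subject (48.0% against 37.5%) reverses the order of active and placebo. That order carries little information anyway: the exact 95% intervals are 27.8% to 68.7% for 12/25 and 15.7% to 84.3% for 4/8.

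**Step 4. How likely is at least one affected subject?** The documents give no rate, so a range is assumed for the share p of subjects with an event whose status depends on the sentence used. The chance of at least one is 1 − (1 − p)^n.

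| Assumed p | n = 6 | n = 33 (all AD) |
|---|---|---|
| 2% | 11% | 49% |
| 5% | 26% | 82% |
| 10% | 47% | 97% |
| 20% | 74% | >99% |

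This shows that the ambiguity could matter at these sizes. It does not show that it did, or in which direction. A corrected count cannot be computed, because the documents give no event-level onset, report or worsening data.

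**The case against.** A reader might infer that the reported TEAE count is wrong, and wrong in both directions. The documents do not support that. No misclassified event is shown, the counts reproduce, and the two possible errors arise under different sentences. If the second governs, worsening reported as a new AE after dosing is counted and the undercount largely disappears. If the first governs, the late-reported pre-dose AE is excluded and the overcount disappears.

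Two further strong readings also fail. The definition does not ignore onset: the first sentence is itself an onset criterion relative to first exposure. Nor can one say that a worsened condition is never treatment-emergent. Comorbidities are recorded as medical history, and if a site enters an aggravation as an AE starting after dosing, that AE can satisfy both sentences. The full protocol may settle how worsening is recorded; only a synopsis is available here.

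It can also be argued that the second sentence is loose wording for events occurring after dosing. Table 5 names start and end times and no report date, and listings are ordered by onset. Safety information is not lost either: all AE data are listed, and laboratory, vital-sign and ECG changes are summarised separately. TEAEs are one of five primary safety components.

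All of this limits the consequence. It leaves the defect standing: as written, the two rules give opposite answers for a foreseeable event, and no text chooses between them. The point about available data supports the fix, since onset classification is already feasible. The one-subject shifts would apply to any reclassification in groups this small. They describe how fragile the proportions are, not how often this wording would alter them.

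**Conclusion.** The point holds as a conflict in the definition, with a numerical effect that cannot be established. Section 8.1 contains two incompatible criteria and no provision for worsening, so TEAE counts may be too low or too high depending on which sentence was programmed. If one subject were reclassified, a six-subject dose group would move by 16.7 points, Cohort 1 by 14.3, pooled AD placebo by 12.5 and all AD subjects on AL001 by 4.0.

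The conclusion rests on the wording of SAP 8.1 alone. The Cohort 1 denominator of 7 is inferred from the synopsis percentages. The 2% to 20% rates are assumptions. A worsening clause in the full protocol's AE definition cannot be excluded, but it would not remove the contradiction in the SAP. Because AEs are part of the primary endpoint set and the remedy is small, the correction should be made.

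**What to change.** Replace both sentences with one rule:

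- A TEAE is an AE with onset at or after the first dose, or an AE present before the first dose that increases in intensity at or after it.
- Worsening of a medical-history condition is recorded as an AE dated at the worsening.
- Classification uses the date and time of onset or worsening, not the time of report.
- If the timing is incomplete, the event counts as treatment-emergent.

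The synopsis shows the study as completed, so the sponsor should also state which sentence was programmed, re-derive the flag from the existing AE start times and intensities, and report any counts that change, by dose group and for pooled placebo.

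The cost is a short change of SAP text and one derived flag, with the affected tables rerun. The limit is in the data. Worsening that sites recorded neither as an AE nor as a change in intensity cannot be recovered. SAP Table 4 lists medical history as findings only, with no intensity from which to detect it. The report should say so.

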8.2 Adverse Events of Special Interest (AESI)

Adverse events of special interest (AESI) for this study is upper gastrointestinal upset (lower gastrointestinal; diarrhea). The number and percentage of subjects with an AESI, as well as the total number of AESIs, will be summarized for each cohort and overall by SOC and PT.

8.3 Clinical Laboratory Evaluations

Laboratory data will be presented using units as reported by the clinical laboratory. Specific hematology, chemistry, and urinalysis parameters are listed in Table 6.

Table 6: Clinical Laboratory Evaluations

Hematology	Serum chemistry
Complete blood count including: Red blood cells (RBCs), hemoglobin, hematocrit, reticulocytes, mean corpuscular volume, mean corpuscular hemoglobin, mean corpuscular hemoglobin concentration, platelet count	Albumin Alanine aminotransferase (ALT) Aspartate aminotransferase (AST) Alkaline phosphatase (ALP) Blood Urea Nitrogen (BUN) or Urea Bicarbonate Creatinine Electrolytes (Na, K, Cl, Ca, P) Glucose (fasting) Lactate dehydrogenase (LDH) Total bilirubin Direct bilirubin Total cholesterol, High-density lipoprotein (HDL) ^c Low-density lipoprotein (LDL) ^c Triglycerides ^c TSH ^a Mg
White blood cell (WBC) count with differential including (absolute and percentage): neutrophils, lymphocytes, monocytes, eosinophils, basophils, band neutrophils	
HbA1c ^a	

	Vitamin B12 ^a
Urinalysis	
Urobilinogen Glucose Ketones Bilirubin Protein Nitrate Leukocytes Blood pH Specific gravity	

Abbreviations: TSH = thyroid-stimulating hormone.

- a. Performed at Screening and Day 23 or early termination only.
- b. Urobilinogen may be measured via a urine dipstick test at the site if their local laboratory does not include it in their urinalysis panel.
- c. Lipid panel (total cholesterol, high-density lipoprotein, low-density lipoprotein, and triglycerides) measured at the Screening Visit does not need to be repeated on Day -1.

Absolute values for continuous parameters (hematology, general biochemistry, and urinalysis) will be summarized using descriptive statistics by each cohort (dose level of AL001 and pooled placebo; overall) and change from baseline will be presented.

Number (Percentage) of Subjects with Normal, Abnormal Clinically Significant (CS) and Abnormal Non-Clinically Significant (NCS) values will be presented for each laboratory category by each cohort (dose level of AL001 and pooled placebo, overall) and visit.

Serology, alcohol/drug screen, pregnancy test results will be presented in separate listings.

Data listings will include out-of-range flags (Low, High) and whether the abnormal values are clinically significant or not.

8.4 Vital Signs

Vital signs will include heart rate, blood pressure, and body temperature.

Absolute values in vital signs measurements will be summarized descriptively by each cohort (dose level of AL001 and pooled placebo; overall), time point and change from baseline will be presented.

Number (%) of subjects with Normal, Abnormal Clinically Significant (CS) and Abnormal Non-Clinically Significant (NCS) values of vital signs will be presented by each cohort (dose level of AL001 and pooled placebo, overall), visit and time point.

Data listing will identify if values are “abnormal, clinically significant” or “abnormal, not clinically significant”. Vital sign results will be presented.

8.5 Physical Examination Findings

The physical examination will include a general review of the following body systems (at minimum): general appearance, head and neck, cardiovascular, respiratory, abdomen, and brief neurological examination.

Physical examination results will be listed as normal or abnormal. Abnormal findings of clinical significance will be included in the listing.

8.6 12-lead Electrocardiogram

12- Lead safety ECG results will be summarized descriptively by each cohort ((dose level of AL001 and pooled placebo, overall), time point and change from baseline will be presented.

Number (%) of subjects with Normal, Abnormal Clinically Significant (CS) and Abnormal Non-Clinically Significant (NCS) values of ECG will be presented by each cohort (dose level of AL001 and pooled placebo, overall), visit and time point.

Data listing will identify if values are “abnormal, clinically significant” or “abnormal, not clinically significant”.

9 DATA HANDLING AND PRESENTATION

All safety and statistical outputs will be generated using SAS software, version 9.4.

All programs used to generate statistical analyses will be validated according to Altasciences's standard operating procedure (SOPs).

Tables, figures and listings will be provided in RTF formats.

9.1 Safety Analysis Presentation

Adverse events and medical history will be classified using the MedDRA terminology as defined in the study data management plan (DMP).

Prior and concomitant medications will be coded with the World Health Organization drug dictionary (WHO-DD) (March 2022 B3) as defined in the study DMP.

Generally, summaries will be presented by cohort (dose level of AL001 and pooled placebo, overall). Some summaries will also be presented to include overall (i.e., subject disposition and demographics) Also, applicable safety data will be presented by combined active and pooled placebo groups, such as, disposition, demographic, adverse events, labs, vital signs, and 12-ECG data.

Summaries for data collected at scheduled times specified in the protocol will be presented by cohort (dose level of AL001 and pooled placebo, overall), visit, and, where applicable, time point. Continuous variables will be summarized using the number of observations, mean, standard deviation, minimum, median, and maximum. Categorical variables will be summarized using the number of observations and the corresponding percentage.

In general, the data listings will include data from all subjects who receive at least one dose of either AL001 or placebo.

Study days will be included in adverse event and concomitant medication listings in addition to dates. Study days will be calculated relative to the first day of double-blind treatment (Day 1) derived as (event date - first day of AL001 or placebo dosing) +1 for events after the first day of dosing and (event date - first day of AL001 or placebo dosing) for events before the first day of dosing.

The following general comments also apply to all statistical analyses and data presentations:

- Duration variables will be calculated using the general formula: (end date - start date) +1.
- If the reported value of a clinical laboratory parameter cannot be used in a statistical summary table (e.g., a character string is reported for a parameter of the numerical type), a coded value must be appropriately determined and used in the statistical analyses. In general, a value or lower and upper limit of normal range such as ' <10 ' or ' ≤ 5 ' will be treated as '10' or '5' respectively, and a value such as ' >100 ' will be treated as '100'. However, the actual values as reported in the database will be presented in data listings.
- When assessments are repeated for a given time point or performed at unscheduled times, only the result which is the closest to the dosing time will be included in summary tables.

In general, summary statistics for raw variables (i.e., variables measured at the study site or central laboratory) will be displayed as follows:

- Minima and maxima will be displayed to the same number of decimal places as the raw data.
- Means, medians, and quartiles will be displayed to 1 additional decimal place.
- Standard deviations will be displayed to 2 additional decimal places.
- Percentages will be displayed to 1 decimal place. Percentages between 0 and 0.1 (exclusive) will be displayed as ‘<0.1’.
- P-values will be displayed to 3 decimal places. P-values that are less than 0.001 will be displayed as ‘<0.001’ if applicable.

The number of decimal places for summary statistics of derived variables (i.e., variables that are not measured by the study site but are calculated for analysis based on other measured variables) will be determined on a case by case basis. In general:

- Minima and maxima will be displayed to the commonly used unit of precision for the parameter.
- Means, medians, quartiles, and confidence limits will be displayed to 1 additional decimal place.
- Standard deviations will be displayed to 2 additional decimal places.

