9.2 Baseline

The baseline is defined as the most recent non-missing measurement (scheduled or unscheduled) collected before the first dose of study drug in each cohort.

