APPENDIX A STUDY SCHEDULE(S)

Study Procedures	Screening (28 days prior to randomization)	In-patient admission	Treatment Period		Clinic Discharge	Follow-up Period		Early Termination (ET)
Study Day	Days -28 to -1	Day -1	Day 1	Days 2 to 14	Day 15	Day 23 ±1 day Clinic Visit	Day 42 ±2 days Telephone call	
Informed Consent	X							
Admission ¹		X						
Clinic Confinement			X	X				
Discharge					X			
Medical and Surgical History	X							
Physical Examination	X				X	X		X
Demographic information	X							
Body Height/Body Weight	X							
Vital Signs ²	X	X	X	X	X	X		X
12-lead ECG ³	X		X	X	X	X		X

¹ Subjects will be admitted to the clinical research unit at least 16 hours prior to the first study drug administration.

² Vital signs will include blood pressure, heart rate and oral body temperature. On Days 1 to 14, vital signs will be measured within 1 hour prior to dosing using the same arm, if possible, after 5 minutes in seated position.

Study Procedures	Screening (28 days prior to randomization)	In-patient admission	Treatment Period		Clinic Discharge	Follow-up Period		Early Termination (ET)
Study Day	Days -28 to -1	Day -1	Day 1	Days 2 to 14	Day 15	Day 23 ±1 day Clinic Visit	Day 42 ±2 days Telephone call	
Safety Laboratory Tests ⁴	X	X		X	X	X		X
Serology (HIV/HBV/HCV)	X							
Serum Pregnancy Test (females of childbearing potential only)	X							
Urine Pregnancy Test (females of childbearing potential only)		X						
COVID-19 Test ⁵	X	X						
Urine Drug Screen and Alcohol Breath or Urine Test	X	X						
Inclusion/Exclusion Criteria	X	X						
Randomization			X					
Fasted Study Drug			X	X				

³ On Day 1, ECGs will be conducted pre-dose and 1 hour (±10 minutes) after the third dose of Day 1. On Days 7, 13, and 14, ECGs will be performed prior to first daily dose.

⁴ Safety laboratory tests (chemistry, hematology, and urinalysis) will be performed on Day -1, Day 7 (pre-dose), Day 15, and Day 23. For all subjects, total cholesterol, high-density lipoprotein, low-density lipoprotein, and triglycerides will not be included in the safety laboratory tests performed on Day -1. For subjects who are screened within 5 days of check-in (on Day -6 to Day -2), the safety laboratory tests will not be performed on Day -1.

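### Keeping only the result closest to dosing lets a pre-dose repeat replace the original, so by-visit safety counts can miss transient abnormalities, and no worst-value count is planned to recover them

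*SAP*

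**What the plan says.** SAP 9.1 sets one selection rule for assessments that are repeated at a time point or done at unscheduled times: "only the result which is the closest to the dosing time will be included in summary tables". The SAP text appears twice in the file, and the rule is the same in both copies. It stands among general comments that are said to cover all analyses and presentations, and no safety table is exempted.

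Appendix A fixes the timing of the affected assessments:

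- Vital signs, Days 1 to 14: "vital signs will be measured within 1 hour prior to dosing".
- ECGs: "On Days 7, 13, and 14, ECGs will be performed prior to first daily dose". Day 1 has a pre-dose ECG and one about an hour after the third dose. ECGs are also scheduled for Day 15 and Day 23.
- Safety laboratory tests: "will be performed on Day -1, Day 7 (pre-dose), Day 15, and Day 23".

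The categorical tables split subjects into normal, abnormal not clinically significant (NCS) and abnormal clinically significant (CS):

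- Laboratory tests (8.3): "values will be presented for each laboratory category by each cohort (dose level of AL001 and pooled placebo, overall) and visit".
- Vital signs (8.4): "values of vital signs will be presented by each cohort (dose level of AL001 and pooled placebo, overall), visit and time point".
- ECG (8.6): "values of ECG will be presented by each cohort (dose level of AL001 and pooled placebo, overall), visit and time point".

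None of these sections adds a count of subjects with any abnormal value or with their worst value on treatment. Baseline has its own rule in 9.2: "the most recent non-missing measurement (scheduled or unscheduled) collected before the first dose of study drug in each cohort". Dosing is three times daily (SAP 3.2), and 9.1 does not say which dose is the dosing time.

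**The concern.** The rule chooses by clock time, not by value or validity. At a pre-dose time point, time runs towards the dose, so a second reading taken before that dose is nearer to it than the first. If staff repeat a reading because it was abnormal, the table keeps the second reading and drops the one that prompted it. An unscheduled abnormal result is also dropped when another result for that time point lies nearer to dosing.

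Vital signs, ECGs and safety laboratory tests are listed endpoints of the primary safety objective (SAP Table 1). The normal/NCS/CS tables are the only categorical summaries that SAP 8.3, 8.4 and 8.6 plan for them. With about six AL001 subjects per cohort, one replaced reading can turn one abnormal subject into none.

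**Working it through.** The plan states no figure here, so there is none to reproduce. The checks are on timing, exposure and counts.

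**1. When does the repeat win?** Let the original be *t* minutes before the dose that defines the dosing time, and the repeat *g* minutes later. The repeat is closer when |t − g| < t, that is, when g < 2t.

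- Repeat before that dose (g < t): always closer. Example: t = 40, g = 15 gives 25 against 40.
- Repeat after the dose: closer only if g < 2t. Example: t = 40, g = 90 gives 50 against 40, so the original stays.
- Original after the dose (second ECG on Day 1, about 60 minutes): the repeat lies at 60 + g, so the original stays. Days 15 and 23 behave the same way.
- Reading before the first dose: this is the baseline, governed by 9.2.

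**2. How many scheduled points are exposed?** Counting from after the first dose through Day 15:

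| Assessment | Scheduled points | Exposed |
|---|---|---|
| ECG | Day 1 post-dose, Days 7, 13, 14, 15 = 5 | 3 |
| Laboratory | Days 7, 15 = 2 | 1, only if repeated before the dose |
| Vital signs, once daily before the first dose (assumed) | Days 2–14, 15 = 14 | 13 |
| Vital signs, before every dose (assumed), dosing time = following dose | 3 × 14 − 1 + 1 = 42 | 41 |
| Same, dosing time = first daily dose | 42 | 13 |

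The last two rows show that the undefined term alone moves the exposure from 41 of 42 sets to 13 of 42. The three ECGs are exposed under either meaning.

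**3. Effect on the counts.** Let *p* be the abnormal rate at the first reading, *f* the share of abnormal readings repeated before the dose, and *r* the share of those repeats that are normal. If only abnormal readings are repeated, the tabulated rate is p(1 − f·r). The documents give none of these three values. As an illustration with n = 6, p = 1/3 and f = 1:

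| r | Expected abnormal, first reading | Expected abnormal, tabulated | Chance of showing at least one abnormal |
|---|---|---|---|
| 0.3 | 2.0 | 1.4 | 0.91 → 0.80 |
| 0.5 | 2.0 | 1.0 | 0.91 → 0.67 |
| 0.7 | 2.0 | 0.6 | 0.91 → 0.47 |

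For r = 0.5 the chance goes from 1 − (2/3)^6 = 0.91 to 1 − (5/6)^6 = 0.67. With f = 0 there is no loss.

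**4. Repeats unrelated to value.** Suppose a share *h* of normal readings is also repeated and a share *s* of those repeats is abnormal. The tabulated rate is then p(1 − f·r) + (1 − p)·h·s. If a second reading has the same overall abnormal rate as a first, p·r = (1 − p)·s, and the rate becomes p − p·r·(f − h). With f = h it stays at p. A net understatement therefore needs abnormal readings to be repeated more often than normal ones.

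**5. Weight of one subject.** SAP 3.5 plans six AL001 subjects per cohort: 1/6 = 16.7 points. The protocol synopsis reports 14.3% of AL001 subjects with a treatment-emergent event in Cohort 1, which implies 1 of 7. The four AD cohorts then give 7 + 6 + 6 + 6 = 25 subjects and 1 + 1 + 5 + 5 = 12 with events, matching the reported 12 of 25. So one subject is 1/7 = 14.3 points in Cohort 1, 1/8 = 12.5 in AD pooled placebo and 1/25 = 4.0 in combined AD active.

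**The case against.** **The premise is unseen.** A net understatement needs a value-driven repeat practice, and the documents describe none. The protocol text available is a synopsis, while the SAP rests on protocol version 8.0, whose body may state when to repeat. This stands: the loss can be described but not sized.

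**Little is hidden.** All available data are listed, with CS and NCS marked. Adverse event tables are separate. The safety committee reviews laboratory reports, adverse events, tolerability and PK data, and nothing ties that review to these final tables. A persistent abnormality would show at other time points, so only a transient one is lost. This stands too, and it keeps the point small. It does not restore the value in the summary table.

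**Laboratory reach is minimal.** Only Day 7 is exposed, and a repeat prompted by a reported result would probably be drawn after the dose (an assumption about turnaround). This is accepted.

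**A confirmatory reading may be the better one.** A worst-value count keeps spurious first readings and can saturate. If 10% of vital-sign sets were abnormal and independent (both assumed), 1 − 0.9^14 = 77% of subjects would have at least one abnormal set over 14 sets, and 1 − 0.9^42 = 99% over 42. This is a fair reason not to replace the by-visit counts and to look mainly at the CS category.

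**Stronger readings that the documents do not support.** A reader might infer that the rule always prefers the repeat. It does so for certain only when the repeat precedes the dose that defines the dosing time. A reader might also infer a bias in favour of AL001. The rule treats AL001 and placebo alike, and with equal f and r both rates and their difference shrink by the same factor (1 − f·r). Nor is harm to the PK summaries shown, since Appendix A fixes the scheduled PK sampling times.

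**Conclusion.** The point holds as a cheap improvement to the safety tables, not as an error that invalidates them. At on-treatment pre-dose points, mainly vital signs through Day 14 and ECGs on Days 7, 13 and 14, a repeat taken before the defining dose displaces the original, and unscheduled abnormal results further from dosing are left out. No planned count brings them back.

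Whether the by-visit counts understate transient abnormalities depends on abnormal readings being repeated more often than normal ones, which is assumed. The overall size is unknown. What can be stated is the weight of one displaced subject in the small dose-level cells, and that vital-sign exposure depends on a term the SAP leaves undefined.

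**What to change.** 1. Keep the 9.1 rule for the by-visit summaries, including the by-visit normal/NCS/CS counts, so that each subject still has one defined value per time point.
2. State which of the three daily doses the dosing time means, for example the dose to which the scheduled time point is tied.
3. Add one worst on-treatment category row to the normal/NCS/CS tables in 8.4 and 8.6, and in 8.3 for consistency. Count each subject once, from after the first dose through Day 15, ranking CS above NCS above normal. Use all valid scheduled, repeat and unscheduled results, and exclude only readings flagged as technically invalid, such as an unreadable ECG trace.

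The cost is a few lines of SAP text and one row per table, from data that are already listed. The synopsis gives a study completion date of 2023/05/15, so at this stage the change would be a supplementary table with a documented clarification. The downside is slightly more programming and some spurious first readings counted as abnormal, which makes the CS count the more informative part of the new row.
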